[figure not shown]
[figure not shown]

CLINICAL PROTOCOL

Protocol Number	SCRX001-002
Version and Date	Version 4.0, 18-Nov-2016
Protocol Title	An Open-label, Single-Arm, Phase 2 Study Evaluating the Efficacy, Safety and Pharmacokinetics of Rovalpituzumab Tesirine (SC16LD6.5) for Third-line and Later Treatment of Subjects with Relapsed or Refractory Delta-Like Protein 3-Expressing Small Cell Lung Cancer (TRINITY)
Investigational Drug	Rovalpituzumab tesirine
Phase	2
IND Number	117510
EUDRACT Number	2015-004506-42
Medical Monitor	
Sponsor	
Sponsor Representative	
Sponsor Representative Signature	
SAE Contact Information	See information specified on the SAE reporting manual

This study will be conducted in compliance with the protocol, Good Clinical Practice and all other applicable regulatory requirements, including the archiving of essential documents.

*The specific contact details of the AbbVie legal/regulatory entity (person) within the relevant country are provided within the clinical trial agreement with the Investigator/Institution and in the Clinical Trial Application with the Competent Authority.
“AbbVie” shall mean AbbVie Inc. or its affiliate AbbVie Stemcentrx LLC.

Confidential Information

No use or disclosure outside AbbVie is permitted without prior written authorization from AbbVie.

SYNOPSIS

TITLE: An Open-label, Single-Arm, Phase 2 Study of Rovalpituzumab Tesirine (SC16LD6.5) Evaluating the Efficacy, Safety and Pharmacokinetics for Third-line and Later Treatment of Subjects with Relapsed or Refractory Delta-Like Protein 3-Expressing Small Cell Lung Cancer (TRINITY)	
PROTOCOL NUMBER:	SCRX001-002
PHASE OF DEVELOPMENT:	2
INVESTIGATORS AND STUDY CENTERS: Multicenter	
OBJECTIVES:	
Primary: 
• To investigate the efficacy of rovalpituzumab tesirine as third-line and later treatment for subjects with relapsed or refractory delta-like protein 3 (DLL3)-expressing small cell lung cancer (SCLC)	
Secondary: 
• To assess duration of response, clinical benefit rate and progression-free survival in subjects with relapsed or refractory DLL3-expressing SCLC treated with rovalpituzumab tesirine• To assess the safety and tolerability of rovalpituzumab tesirine• To characterize the pharmacokinetics of rovalpituzumab tesirine and incidence of anti-therapeutic antibodies (ATA)	
Exploratory: 
• To explore relationship of DLL3 expression to clinical outcome during treatment with rovalpituzumab tesirine• To explore the efficacy and safety of rovalpituzumab tesirine retreatment when administered to subjects with DLL3-expressing SCLC who previously achieved clinical benefit on rovalpituzumab tesirine• To explore the effect of rovalpituzumab tesirine on disease biomarkers and pharmacodynamics	
TEST PRODUCTS, DOSE, AND MODE OF ADMINISTRATION:	

• Rovalpituzumab tesirine 0.3 mg/kg intravenously on Day 1 of each 6-week cycle for 2 cycles• Dexamethasone 8 mg orally (PO) twice daily on Day –1, Day 1 (the day of dosing), and Day 2 of each 6-week cycle	
STUDY DESIGN AND METHODOLOGY:	
This is an open-label, single-arm, Phase 2 study of rovalpituzumab tesirine in DLL3-expressing SCLC subjects with relapsed or refractory disease after receiving at least 2 previous regimens, including at least one platinum-based regimen. Only subjects with tumor cell expression that is DLL3 positive based on an immunohistochemistry (IHC) assay specification will be enrolled in the study. Enrollment will continue until up to approximately 123 DLL3 high, third-line subjects are treated. Enrollment will be carried out in two stages. In Stage 1, up to 60 evaluable, DLL3 high (per IHC assay specification), subjects may be enrolled. If among the 60 evaluable, DLL3 high (per IHC assay specification) subjects, more than 9 subjects achieve complete response or partial response, then enrollment will continue to Stage 2. At least 63 additional subjects that are DLL3 high (per IHC assay specification) will be enrolled in Stage 2. Otherwise enrollment will terminate. Of the enrolled DLL3 positive subjects, less than or equal to 30% can be fourth-line or later.	
All enrolled subjects will receive 0.3 mg/kg rovalpituzumab tesirine intravenously (IV) on Day 1 of every six-week treatment cycle for two cycles. An additional two cycles of rovalpituzumab tesirine (retreatment) is permitted for subjects who tolerated their initial two doses of rovalpituzumab tesirine, achieved clinical benefit as defined by stable disease or better, have received no other systemic anti-cancer therapy after rovalpituzumab tesirine as administered per this protocol, and with central radiographic assessment-confirmed disease progression at least 12 weeks after the second dose. Additional retreatment, beyond a total of four cycles will require approval from the Medical Monitor.	

All subjects in the long-term follow-up will continue disease assessments every 6 weeks for 6 months, then every 12 weeks thereafter. Subjects will be followed until disease progression per RECIST (version 1.1) or initiation of new anticancer treatment, whichever occurs first; and will afterwards be followed for survival until death or study termination, whichever occurs first.

Blood samples for PK, immunogenicity, biomarker and pharmacodynamics assessments will be collected at protocol-defined time points to support the study endpoints (see Sections 7.3 and 7.4).

The primary efficacy endpoints of the study will be the best objective response rate at the end of treatment assessment (42 ± 3 days after last dose) and overall survival. Safety will be assessed by pre- and post-treatment measurements of vital signs and clinical laboratory assessments, and through the recording of adverse clinical events. PK and cytokine data will be collected at select sites only.

An independent Data Monitoring Committee (iDMC) will act in an advisory capacity to monitor subject safety and efficacy data from the study.

MAJOR ELIGIBILITY CRITERIA:

Adult subjects with histologically confirmed advanced DLL3+ SCLC with measurable disease, relapsed/refractory to at least 2 prior systemic regimens, including one platinum-based regimen; ECOG 0-1; adequate hematologic, hepatic and renal function; and no prior exposure to a PBD-based drug (unless retreated with rovalpituzumab tesirine in the context of this protocol).

PLANNED SAMPLE SIZE:

Among the enrolled DLL3 high subjects, at least 123 will be third-line. Of the enrolled, DLL3 positive subjects, less than or equal to 30% can be fourth-line or later.

ENDPOINTS AND OUTCOME MEASURES:

Efficacy Endpoints

Primary:

This study has two co-primary endpoints:

- Objective response rate through the End of Treatment (42 ± 3 days after last dose) for DLL3 high and for DLL3 positive, per IHC assay specification subjects
- Overall survival for DLL3 high and for DLL3 positive, per IHC assay specification subjects

Secondary:

- Duration of response for DLL3 high and for DLL3 positive subjects, per IHC assay specification
- Clinical Benefit Rate for DLL3 high and for DLL3 positive subjects, per IHC assay specification
- Progression-free survival for DLL3 high and for DLL3 positive subjects, per IHC assay specification

Safety Endpoints

Safety assessments include vital signs, body weight, ECOG score, clinical adverse events, laboratory tests (hematology, serum chemistries, urinalysis, and coagulation), ECGs, echocardiogram, fluid retention questionnaire, and monitoring of concomitant therapies.

Pharmacokinetic and Pharmacodynamic Endpoints

Pharmacokinetic assessments will include blood samples for rovalpituzumab tesirine and anti-therapeutic antibodies (ATAs).

Pharmacodynamic and biomarker assessments will include analyses of tumor tissue for DLL3 expression, and of blood samples for tumor markers, [REDACTED] and soluble biomarkers such as soluble DLL3.

STATISTICAL METHODS:

Sample Size

A response rate of 15% or less is typically observed in this advanced state of the disease. It is assumed that at least 25% of subjects treated with rovalpituzumab tesirine will achieve complete or partial response. In Stage 1, up to 60 evaluable, DLL3 high (per IHC assay specification), subjects may be enrolled. In Stage 2, at least 63 additional subjects that are DLL3 high (per IHC assay specification) will be enrolled, to maintain an 80% power at a one-side significance level of 0.025. The number of subjects evaluated at each stage and the minimum

number of responders to continue from Stage 1 to Stage 2 were estimated using the minimax principle of the Simon two-stage design.

Up to approximately 123 DLL3 high, third-line subjects will be enrolled. The total sample size for this study will be determined by the proportion of enrolled subjects with DLL3 high expression among those who are DLL3 positive.

Efficacy Analysis

The primary efficacy endpoint is objective response rate defined as the proportion of subjects whose best overall response is either complete response (CR) or partial response (PR) according to RECIST (version 1.1). The best overall response is the best recorded response through End of Treatment (42 ± 3 days after last dose). The overall response rate will be estimated based on the maximum likelihood estimator (i.e., crude proportion of subjects with best overall response of CR or PR). The estimate will be accompanied by a two-sided exact 95% binomial confidence interval.

Overall survival will be summarized descriptively using the Kaplan-Meier method.

The proportion of subjects alive at 6, 9, and 12 months from the initiation of study treatment will be estimated and summarized using the Kaplan-Meier approach.

Duration of response and progression-free survival will also be summarized descriptively using the Kaplan-Meier method. The progression-free survival rate at additional landmark time points may also be evaluated (e.g., 6, 9, and 12 months).

For subjects retreated with rovalpituzumab tesirine, both safety and selected efficacy outcomes will be analyzed separately from the outcomes observed following the initial course of treatment.

TABLE OF CONTENTS

SYNOPSIS.....	2
DEFINITIONS OF ABBREVIATIONS AND TERMS	10
1 INTRODUCTION	13
1.1 Background.....	13
1.1.1 Small Cell Lung Cancer.....	13
1.1.2 DLL3 and Rovalpituzumab Tesirine	14
1.1.3 Rationale for the Study and Anticipated Risks	14
2 OBJECTIVES AND ENDPOINTS	16
2.1 Objectives	16
2.1.1 Primary Objective	16
2.1.2 Secondary Objectives.....	16
2.1.3 Exploratory Objectives	16
2.2 Endpoints	16
2.2.1 Primary Efficacy Endpoints.....	16
2.2.2 Secondary Efficacy Endpoints.....	16
2.2.3 Safety Endpoints	17
2.2.4 Pharmacokinetics, Biomarker and Pharmacodynamic Endpoints	17
3 INVESTIGATIONAL PLAN.....	18
3.1 Summary of Study Design	18
3.2 Discussion and Rationale for Study Design.....	19
3.2.1 Study Design.....	19
3.2.2 Dose Rationale	19
3.2.3 Blinding.....	20
4 STUDY POPULATION	21
4.1 Inclusion Criteria	21
4.2 Exclusion Criteria	23
4.3 Removal of Subjects from Therapy or Assessment.....	24
4.3.1 Discontinuation of Study Drug	24
4.3.2 Subject Discontinuation from Study	24
5 TREATMENTS	25
5.1 Treatments Administered.....	25

5.2	Investigational Product	25
5.2.1	Description.....	25
5.2.2	Dose and Administration	25
5.2.3	Dose Modifications.....	26
5.2.4	Storage and Handling.....	28

EOT	end of treatment
ESR	erythrocyte sedimentation rate
FDA	Food and Drug Administration
GCP	Good Clinical Practice
GFR	Glomerular Filtration Rate
HBcAb	Hepatitis B core antibody
HBsAb	Hepatitis B surface antibody
HBsAg	Hepatitis B surface antigen
HCV	Hepatitis C virus
HNSTD	highest nonseverely toxic dose
ICF	Informed Consent Form
ICH	International Conference on Harmonisation
iDMC	independent Data Monitoring Committee
IEC	Independent Ethics Committee
IHC	Immunohistochemistry
IHR	infusion or hypersensitivity reaction
IL	interleukin
INR	international normalized ratio
IRB	Institutional Review Board
IUD	intrauterine device
IV	intravenous(ly)
LCNEC	large cell neuroendocrine carcinoma
LTFU	long-term follow-up
LVEF	left ventricular ejection fraction
MedDRA	Medical Dictionary for Regulatory Activities
MDRD	Modification of Diet in Renal Disease
MRI	magnetic resonance imaging
MTD	maximum tolerated dose
NCI	National Cancer Institute
NSCLC	non-small cell lung cancer
NSE	neuron-specific enolase
NYHA	New York Heart Association
ORR	objective response rate
OS	overall survival
PBD	pyrrolobenzodiazepine

Abbreviation or Term	Definition
PCR	polymerase chain reaction
PD	progressive disease
PET	positron emission tomography
PFS	progression-free survival
PK	pharmacokinetics
PO	per os
PR	partial response
PT	prothrombin time
PTT	partial thromboplastin time
q3w	Every 3 weeks
q6wk	Every 6 weeks
QTc	QT interval corrected for heart rate
QTcB	QT interval corrected for heart rate by Bazett's formula
QTcF	QT interval corrected for heart rate by Fridericia's formula
RECIST	Response Evaluation Criteria in Solid Tumors
RF	rheumatoid factor
RP2D	recommended phase 2 dose
SAE	serious adverse event
SC-DR002	DNA cross-linking agent also known as D6.5
SC16	Humanized DLL3-specific IgG1 antibody
SCLC	small cell lung cancer
S _{cr}	serum creatinine
SD	stable disease
SPF	sun protection factor
t _{1/2}	terminal half-life
TEAE	treatment-emergent adverse event
T _{max}	time of maximum concentration
TNBC	triple-negative breast cancer
TPC	Tumor perpetuating cell
ULN	upper limit of normal
USP	United States Pharmacopeia
VEGF	vascular endothelial growth factor
V _{ss}	volume of distribution at steady state

1 INTRODUCTION

1.1 Background

1.1.1 Small Cell Lung Cancer

Small cell lung cancer (SCLC) is an important unmet medical need, representing 15–20% of the 220,000 annual new cases of lung cancer in the United States (Govindan 2006, Siegel 2012).

These cancers arise from epithelial cells with neuroendocrine differentiation and typically are positive for both cytokeratin and neuroendocrine markers; however, the diagnosis is usually made by morphologic examination. Historically, SCLC has been divided into limited versus extensive stage disease—the former being defined as disease limited to the chest that can be encompassed by a radiation field while the latter includes all other cases. Approximately one-third of newly diagnosed patients will have limited stage disease while the rest will be extensive. Unlike nonsmall cell lung cancer (NSCLC), SCLC is rarely cured with local therapy (surgery and/or radiotherapy); systemic chemotherapy remains the cornerstone of therapy for all stages of disease. Standard initial therapy for all patients with a suitable performance status consists of a platinum salt (carboplatin or cisplatin) in combination with a second agent, usually etoposide. For patients with limited stage disease, concurrent or sequential involved-field thoracic radiotherapy is indicated. Response rates to initial therapy are high, ranging from 70–90% for limited stage and 60–70% for extensive stage; however recurrence rates are also high in the limited group and universal in the extensive group, leading to median survivals of 14–20 months and 9–11 months, respectively (Simon 2004).

Recurrent SCLC is rapidly fatal (median survival less than 6 months). Two groups may be identified: ‘resistant’ patients who recur during or within 2–3 months after completing a course of initial therapy, and ‘sensitive’ patients who recur later following primary therapy. Although many single agents and chemotherapy combinations have shown some transient evidence of activity in recurrent patients, only topotecan has received FDA approval in this setting. The approval for an intravenous (IV) formulation of topotecan was based on response rates of 11–31% in the sensitive population and between 2–7% in the refractory population, with an overall time to progression (TTP) of 3–4 months (Eckardt 2007, Owonikoko 2012). An oral formulation was later approved for patients based on a survival benefit compared with best supportive care (25.9 versus 13.9 weeks, hazard ratio = 0.64). The overall response rate (ORR) in

this study was 7% (O'Brien 2006). There is no approved agent, nor an existing standard of care treatment, for SCLC patients who recur following second-line treatment.

1.1.2 DLL3 and Rovalpituzumab Tesirine

Delta-like protein 3 (DLL3) is an inhibitory ligand of the Notch receptor family. It is highly expressed in SCLC and some neuroendocrine cancers like large cell neuroendocrine carcinoma (LCNEC), including tumor perpetuating cells (TPCs), but with no detectable expression in normal tissues or other non-neuroendocrine tumor types. While the function of DLL3 has not been clearly defined, it has been implicated in the regulation of cell development and fate decisions (Dunwoodie 1997, Chapman 2011).

Rovalpituzumab tesirine is a DLL3-targeted ADC consisting of the humanized DLL3-specific IgG1 antibody SC16; the DNA cross-linking agent SC-DR002 (D6.5); and a protease-cleavable linker that covalently links SC-DR002 to SC16. The primary mechanism of rovalpituzumab tesirine is binding of the ADC to DLL3 on target-expressing cells, followed by internalization of the ADC-DLL3 complex and release of SC-DR002 via proteolytic cleavage in late endosomes. Interstrand crosslinks of cellular DNA induced by intercalated SC-DR002 leads to cellular cytotoxicity. ADCs like rovalpituzumab tesirine represent a potential advantage over traditional chemotherapy by delivering cytotoxic agents to specific target cells, resulting in an improved safety profile.

Preliminary data from a Phase 1 study with rovalpituzumab tesirine have been encouraging, with an objective response rate (ORR) of 44% and clinical benefit rate (CBR) of 76% in relapsed or refractory DLL3^{hi} SCLC subjects treated in the expansion cohorts of 0.2 mg/kg q3wk and 0.3 mg/kg q6wk, and preserved response rates in the subset of third line subjects (ORR 45%, CBR 73%). In all expansion cohort SCLC subjects, regardless of DLL3 expression, the ORR and CBR were 23% and 68%, respectively (AbbVie data on file).

1.1.3 Rationale for the Study and Anticipated Risks

No approved therapeutic options are available for subjects who have progressive SCLC following treatment with two prior therapies, including at least one involving a platinum-based frontline regimen. Based on the promising efficacy data to date, rovalpituzumab tesirine warrants investigation as a potentially important therapeutic option in the third-line and later setting. This

study will examine the therapeutic utility of rovalpituzumab tesirine in subjects with DLL3+ extensive-stage SCLC after failure of at least two prior systemic regimens, including a platinum-based therapy.

Potential risks with rovalpituzumab tesirine include fatigue, dyspnea, and nausea, which have been the most frequently reported AEs to date. However, remarkable toxicities have included serosal effusions (typically pleural or pericardial), peripheral edema, cutaneous reactions (typically photosensitivity), and thrombocytopenia. In addition, preclinical toxicology studies conducted in the rat and the cynomolgus monkey have identified the lung and kidney as a potential source of clinical AEs. Accordingly, safety assessments will include regular assessments at protocol-specified time points of routine physical examination, laboratory and imaging tests, as well as echocardiograms, a fluid retention questionnaire, daily weights and spot urine protein testing.

2 OBJECTIVES AND ENDPOINTS

2.1 Objectives

2.1.1 Primary Objective

- To investigate the efficacy of rovalpituzumab tesirine as third-line and later treatment for subjects with relapsed or refractory delta-like protein 3 (DLL3 -expressing small cell lung cancer (SCLC)

2.1.2 Secondary Objectives

- To assess duration of response, clinical benefit rate and progression-free survival in subjects with relapsed or refractory DLL3-expressing SCLC treated with rovalpituzumab tesirine
- To assess the safety and tolerability of rovalpituzumab tesirine
- To characterize the pharmacokinetics of and incidence of anti-therapeutic antibodies (ATA) to rovalpituzumab tesirine

2.1.3 Exploratory Objectives

- To explore relationship of DLL3 expression to clinical outcome during treatment with rovalpituzumab tesirine
- To explore the efficacy and safety of rovalpituzumab tesirine retreatment when administered to subjects with DLL3-expressing SCLC who previously achieved clinical benefit on rovalpituzumab tesirine
- To explore the effect of rovalpituzumab tesirine on disease biomarkers and pharmacodynamics

2.2 Endpoints

2.2.1 Primary Efficacy Endpoints

This study has two primary endpoints:

- Objective response rate through the End of Treatment (42 ± 3 days after last dose) for DLL3 high and for DLL3 positive subjects, per IHC assay specification
- Overall survival for DLL3 high and for DLL3 positive subjects, per IHC assay specification

2.2.2 Secondary Efficacy Endpoints

- Clinical Benefit Rate for DLL3 high and for DLL3 positive subjects, per IHC assay specification

- Duration of response for DLL3 high and for DLL3 positive subjects, per IHC assay specification
- Progression-free survival for DLL3 high and for DLL3 positive subjects, per IHC assay specification

2.2.3 Safety Endpoints

- Adverse Events
- Vital signs
- Laboratory abnormalities
- Electrocardiographic intervals (e.g. QTc)
- Echocardiography
- Components of a fluid retention questionnaire

2.2.4 Pharmacokinetics, Biomarker and Pharmacodynamic Endpoints

- Specific pharmacokinetic parameters of rovalpituzumab tesirine (e.g., C_{max} , AUC)
- Anti-therapeutic antibodies against rovalpituzumab tesirine
- Tumor DLL3 expression
- Inflammatory Markers
- Blood Tumor Markers
- Biomarkers, including soluble DLL3

3 INVESTIGATIONAL PLAN

3.1 Summary of Study Design

This is an open-label, single-arm, multicenter, Phase 2 study of rovalpituzumab tesirine in DLL3-expressing SCLC subjects with relapsed or refractory disease after receiving at least 2 previous regimens, including one platinum-based regimen. Only subjects with tumor cell expression that is DLL3 positive, based on an immunohistochemistry (IHC) assay specification will be enrolled in the study.

All enrolled subjects will receive 0.3 mg/kg rovalpituzumab tesirine once every six-week treatment cycle administered intravenously (IV) for up to two cycles. An additional two cycles of rovalpituzumab tesirine (retreatment) is permitted for subjects who tolerated their initial two doses of rovalpituzumab tesirine, achieved clinical benefit as defined by stable disease or better, have received no other systemic anti-cancer therapy after rovalpituzumab tesirine as administered in this protocol, and with central radiographic assessment-confirmed disease progression at least 12 weeks after the second dose. Additional retreatment, beyond a total of four cycles will require approval from the Medical Monitor.

All subjects in LTFU will continue disease assessments every 6 weeks until 6 months, then every 12 weeks. Subjects will be followed until disease progression per RECIST or initiation of new anticancer treatment, whichever occurs first; and will afterwards be followed for survival until death or study termination, whichever occurs first. Blood samples for PK, immunogenicity, biomarker and pharmacodynamics assessments will be collected at protocol-defined time points to support the study endpoints (see Sections 7.3 and 7.4).

The primary efficacy endpoint of the study will be the best objective response rate through the end of treatment assessment (42 ± 3 days after last dose). Safety will be assessed by pre- and post-treatment measurements of vital signs and clinical laboratory assessments, and through the recording of adverse clinical events. PK and cytokine data will be collected at select sites only.

An independent Data Monitoring Committee (iDMC) will act in an advisory capacity to monitor subject safety and efficacy data from the study.

Retreatment with rovalpituzumab tesirine is permitted for subjects who tolerate two doses of rovalpituzumab tesirine, achieve clinical benefit as defined by stable disease or better, have received no other systemic anti-cancer therapy after rovalpituzumab tesirine as administered in this protocol, and with central radiographic assessment-confirmed disease progression at least 12 weeks after the second dose. Retreatment consists of rovalpituzumab tesirine 0.3 mg/kg IV once every 6 weeks for two cycles, or a reduced dose if dose reduction has previously taken place (see Section 5.2.3.2). Additional retreatment, beyond a total of four cycles will require approval from the Medical Monitor.

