3.2.2 Dose Rationale

The chosen dose regimen, two doses of 0.3 mg/kg administered 6 weeks apart, is based on the safety and efficacy observed in a previous phase 1 study (SCRX16-001), where delayed and/or cumulative toxicities were observed with both q3wk and q6wk schedules and appeared to be related to total dose administered. The total dose was therefore capped at a total cumulative dose of 0.6 mg/kg and the finite dosing regimens of 0.2 mg/kg q3wk for a total of 3 doses (q3wk x 3) and 0.3 mg/kg q6wk for a total of 2 doses (q6wk x 2) were evaluated in expansion cohorts.

Because the intended mechanism of action of rovalpituzumab tesirine is to target cancer stem

cells and, more broadly, tumor-initiating cells, limiting the number of doses is hypothesized to affect anti-tumor response only minimally.

The 0.2 mg/kg q3wk x 3 and 0.3 mg/kg q6wk x 2 dosing regimens demonstrated comparable objective response and clinical benefit rates. Both regimens were tolerated, but the 0.3 mg/kg regimen demonstrated a trend towards lower rates of treatment-emergent adverse events (TEAE), related TEAEs, Grade 3/4 TEAEs and related Grade 3/4 TEAEs. In addition, although the 0.3 mg/kg regimen appeared to have a higher incidence of Grade 3/4 thrombocytopenia, such an AE was generally clinically manageable.

██████████ serosal effusions, which may be life threatening such as leading to pericardial tamponade. In addition, objectives responses preliminarily have appeared to be more durable in subjects treated with the 0.3 mg/kg regimen. Finally, the 0.3 mg/kg q6wk x 2 regimen is more conveniently administered than 0.2 mg/kg q3w x 3 and coincides with the timing of radiographic evaluation of tumor size. Therefore, 0.3 mg/kg q6wk x 2 is the chosen dose regimen for this study.

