5.2.3.2 Dose Reduction Guidelines

Rovalpituzumab tesirine dose reduction for specific toxicities should occur as outlined in Table 5-1 and Table 5-2. If toxicities persist despite dose reduction, the dose should be discontinued. Exceptions to the dose modification guidelines may be permitted with written or electronic approval from the Medical Monitor. If a dose is reduced during the previous cycle, the reduced dose will be administered on Day 1 of subsequent cycles.

Table 5-1 Dose Reductions for Rovalpituzumab Tesirine

Starting Dose	First Dose Reduction (reduce dose)	Second Dose Reduction (discontinue dose)
0.3 mg/kg	0.2 mg/kg	Discontinue dosing

Table 5-2 Unacceptable Toxicities Requiring Dose Reduction

Toxicity	Grade ^a / Details
Thrombocytopenia	Grade 4 thrombocytopenia (or Grade 3 thrombocytopenia with bleeding) lasting more than 7 days and/or requiring platelet transfusion
Thrombocytopenia with bleeding	
Neutropenia	Grade 4 neutropenia lasting more than 7 days and/or requiring hematopoietic growth factor rescue, or any febrile neutropenia (Grade 3 or 4 neutropenia with concurrent fever $\geq 38.3^{\circ}\text{C}$)
Febrile neutropenia	
Laboratory abnormality	Grade 2 or higher hypoalbuminemia (in subject with normal baseline albumin levels) Grade 3 or 4 non-albumin laboratory abnormality considered clinically significant and treatment-related
Nonlaboratory toxicity	Grade 3 or 4 nonlaboratory toxicity (including infusion reactions) with the exception of fatigue, asthenia, nausea, or other manageable constitutional symptom
Skin toxicity	Grade 3 or higher cutaneous toxicity or symptom of photosensitivity (refer to Section 5.5.2)
Serosal effusions	Serosal effusions including: Grade 3 or higher pericardial effusion Grade 2 or higher pleural effusion Grade 3 or higher peripheral edema

a) Refer to Appendix 12.5 for definitions of NCI-CTCAE severity grades.

For the purposes of dose reduction, unacceptable toxicity is defined in Table 5-2. If unacceptable toxicity is encountered in Cycle 1, the Cycle 2 dose may be reduced (Table 5-1). If unacceptable toxicity is encountered at the reduced dose level, treatment should be discontinued. If the rovalpituzumab tesirine dose is reduced, the reduced dose level will be used for any subsequent cycles (i.e., retreatment).

Treatment guidelines for hematologic toxicities, and recommended actions regarding rovalpituzumab tesirine dosing, are outlined in Table 5-3.

Table 5-3 Guidelines for Hematologic Toxicities

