Toxicity	Recommended Action ^a for Rovalpituzumab Tesirine Doses
Toxicity on Day 1 of Cycle (i.e., predose of Cycle 2)	
Platelets < 75,000/ μ L	
 • Hold • With resolution restart at original dose for next cycle • If no resolution, reduce dosing
ANC < 1,000/ μ L	
 • Hold • Growth factors are recommended to be used per ASCO/NCCN/institutional guidelines • With resolution restart at original dose for next cycle • If no resolution, reduce dosing
Toxicity on Subsequent Days of Cycle	
Platelets < 25,000/ μ L for greater than 7 days, OR Thrombocytopenia with bleeding observed in the previous cycle	
 • Hold • With resolution restart at reduced dose per Table 5-1 for next cycle • If no resolution, discontinue dosing
ANC < 500/ μ L for greater than 7 days, OR Neutropenic fever (ANC < 1,000/ μ L and single temperature > 38.3°C or temperature > 38.0°C for more than 1 hour)	
 • Hold • Growth factors are recommended to be used per ASCO/NCCN/institutional guidelines^b • With resolution restart at reduced dose per Table 5-1 for next cycle • If no resolution, discontinue dosing

Abbreviations: ANC = absolute neutrophil count.

- a) The maximum allowed dose interruption is 6 weeks.
- b) Colony stimulating factors include filgrastim or sargramostim

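### The protocol gives conflicting readings of the retreatment dose when the first unacceptable toxicity appears after the second 0.3 mg/kg dose

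*Protocol*

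**What the plan says.** The following parts of the protocol bear on the dose at the first retreatment cycle.

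- **Section 3.1, dose.** Retreatment is "rovalpituzumab tesirine 0.3 mg/kg IV once every 6 weeks for two cycles, or a reduced dose if dose reduction has previously taken place". The sentence ends with a cross-reference to Section 5.2.3.2.
- **Section 3.1, who qualifies.** One paragraph admits "subjects who tolerated their initial two doses of rovalpituzumab tesirine". Another says "Retreatment with rovalpituzumab tesirine is permitted for subjects who tolerate two doses of rovalpituzumab tesirine". Both also require "central radiographic assessment-confirmed disease progression at least 12 weeks after the second dose". Neither defines tolerance.
- **Section 5.2.3.2, general instruction.** "Rovalpituzumab tesirine dose reduction for specific toxicities should occur as outlined in Table 5-1 and Table 5-2". The title of Table 5-2 describes its entries as *requiring* a reduction, and the table names no cycle. Table 5-1 has one step down, from 0.3 to 0.2 mg/kg, and then discontinuation.
- **Section 5.2.3.2, sentence applying Table 5-2.** "If unacceptable toxicity is encountered in Cycle 1, the Cycle 2 dose may be reduced (Table 5-1"). The same paragraph carries a reduced level forward to later cycles and names retreatment as such a cycle, but only where the dose has been reduced. Elsewhere the section lets the Medical Monitor approve exceptions.
- **Table 5-3, hematologic events on later days of a cycle.** "With resolution restart at reduced dose per Table 5-1 for next cycle". The column is headed as recommended action, and a footnote limits interruption to 6 weeks.
- **Section 5.5.2, Table 5-4.** A dose reduction is listed for Grade 3 and Grade 4 photosensitivity, with no limit by cycle.

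**The concern.** The reduction rules are written for a two-dose course in which toxicity after dose 1 changes dose 2. Retreatment adds a dose after dose 2, and no sentence says what that dose is when the toxicity first appears after dose 2. The general rules then point in different directions.

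The case is foreseeable from the protocol's own dose rationale. Section 3.2.2 reports that in phase 1 "delayed and/or cumulative toxicities were observed with both q3wk and q6wk schedules and appeared to be related to total dose administered". Section 5.5.1 describes serosal effusions as potentially life-threatening. Two sites that each follow the text could re-challenge like subjects at different doses, or one could retreat and the other not.

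Safety is the main stake. There is also an analytic one. Retreatment efficacy and safety are an exploratory objective, and the protocol and SAP (Section 5.1) define a separate retreatment population. Two dose levels in that population are planned. Variation that arises only because sites read the text differently is not planned, and it is avoidable.

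**Working it through.** The documents state no figure to reproduce. The check is to follow one subject through each passage and then add up the doses.

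**Subject.** Two infusions at 0.3 mg/kg; first Table 5-2 toxicity after the second; recovery; centrally confirmed progression at least 12 weeks after dose 2; all other retreatment conditions met.

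**Step 1: has a reduction previously taken place?** No. Dose 2 was full, and the initial course has no dose 3. The Section 3.1 exception is not triggered, so its literal result is 0.3 mg/kg.

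**Step 2: does the cross-reference to Section 5.2.3.2 settle it?** Not clearly. The general sentence there (reduction should occur) and the title of Table 5-2 (*requiring*) point to 0.2 mg/kg. The sentence that applies the table speaks only of Cycle 1 toxicity and the Cycle 2 dose, and says *may*. The carry-forward to retreatment depends on a reduction having been made.

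**Step 3: do the tables settle it?** Table 5-3, for its hematologic events, points to the lower dose in the next cycle. Its block for later days of a cycle is not tied to a particular cycle, whereas the block above it is tied to the Cycle 2 predose check. Table 5-4 points to a reduction for severe photosensitivity, so the question is not only hematologic.

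**Step 4: does the tolerance condition remove the subject?** Possibly. If tolerated means free of Table 5-2 toxicity, the subject is not retreated. However, Section 5.2.3.2 carries a reduction made for unacceptable Cycle 1 toxicity forward to retreatment, which implies that some subjects with such toxicity can be retreated. The documents do not decide between these readings.

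**Step 5: do other checks set the dose?** No. Section 4 requires retreated subjects to meet the eligibility criteria again, including recovery to Grade 1. Section 5.2.2 sets dosing-day criteria. Both decide whether to dose, not how much.

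**Arithmetic** (dose levels from Section 3.1 and Table 5-1; two retreatment infusions; initial course 2 × 0.3 = 0.6 mg/kg):

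| Reading | Retreatment | Cumulative |
|---|---|---|
| Section 3.1, literal | 2 × 0.3 = 0.6 mg/kg | 0.6 + 0.6 = 1.2 mg/kg |
| Section 5.2.3.2 general sentence and tables, first retreatment cycle taken as the next cycle | 2 × 0.2 = 0.4 mg/kg | 0.6 + 0.4 = 1.0 mg/kg |
| Strict meaning of tolerated | none | 0.6 mg/kg |

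The first two readings differ by a factor of 0.3/0.2 = 1.5 per infusion.

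**The case against.** The strongest reply is that this is a silent case and not a contradiction. Several parts of that reply stand.

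- **The tables do not strictly require 0.2 mg/kg at retreatment.** A reader might infer that they do from the title of Table 5-2. But the applying sentence is permissive, Table 5-3 gives recommendations, exceptions are allowed, and Table 5-2 names no cycle. This stands, although *may* against *requiring* is itself an inconsistency within Section 5.2.3.2.
- **Table 5-3 fits retreatment poorly.** It is hematologic only and assumes a held dose with at most 6 weeks of interruption. Retreatment starts at least 12 weeks after dose 2, so at least 12 − 6 = 6 weeks after a next cycle would have been due. This stands as a reason for caution. It does not settle the dose, because applying that limit to the gap would bar practically all retreatment.
- **The tolerance condition may exclude the subject.** It cannot be said that tolerated must allow Table 5-2 toxicity merely because reduced subjects can be retreated. Table 5-3 also reduces the dose for unresolved low predose counts, which are not in themselves Table 5-2 events. The strict reading stays open, which is why no retreatment is one of the three outcomes.
- **Section 3.1 may defer to Section 5.2.3.2.** It may, but that section does not give a single answer for toxicity after dose 2.

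A reader might also see a second conflict for toxicity at an already reduced Cycle 2 dose. The documents do not clearly support this. Section 5.2.3.2 and Table 5-1 both say to discontinue, and Section 3.1 only permits retreatment and refers back to that section.

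**Conclusion.** The point holds as an unaddressed case with conflicting literal readings. For a subject whose first unacceptable toxicity follows the second full dose and resolves, the text allows retreatment at 0.3 mg/kg, retreatment at 0.2 mg/kg, or none. Cumulative doses are 1.2, 1.0 and 0.6 mg/kg, and the two retreatment readings differ by 50% per infusion. These figures assume two retreatment infusions and no dosing beyond four cycles. Because the readings lead to different handling of the same subject on a safety matter, this should be corrected. It does not affect the primary analysis.

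Two stronger inferences are not supported. Section 3.2.2 makes late toxicity foreseeable but gives no frequency for first onset after dose 2, so the case cannot be called common. The 0.6 mg/kg cap described there explains the choice of the finite regimens. The protocol openly permits retreatment beyond it, and both retreatment readings exceed it, so it does not help to choose between them.

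No view is taken on which dose or eligibility rule is right.

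**What to change.** Reconcile the retreatment paragraphs of Section 3.1 (and the matching Synopsis text), the text of Section 5.2.3.2 with Tables 5-1 to 5-3, and Table 5-4 in Section 5.5.2. The result should be one rule, chosen by the sponsor, for retreatment eligibility and dose when unacceptable toxicity arises after the second dose. The same edit should resolve *may* against *requiring* within Section 5.2.3.2, say whether the first retreatment cycle counts as the next cycle in Table 5-3, and state what tolerated means.

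This needs a few sentences in a clarification or amendment and no new data collection. The downside is that the retreatment dose or eligibility of some subjects may change.
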